**Aim #3) Compare operative ventilation as measured by average tidal volume (ml) between groups.**

Approved Date: September 3, 2020  
Expiration Date: September 2, 2021  
OhioHealth Corporation  
Institutional Review Board 1

Tidal volume is the lung volume representing the normal volume of air displaced between normal inspiration and expiration when extra effort is not applied (i.e., normal/resting breathing), and is measured continuously throughout the procedure by Anesthesia. Potential patient benefits to a lower pneumoperitoneal insufflation pressure include decreased postoperative pain and improved intraoperative ventilation. The average tidal volume for each patient will be compared between the two groups using independent sample t-test or Mann-Whitney U test, as appropriate.

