Since first described in 2001, robotic assisted laparoscopic prostatectomy (RALP) has been traditionally performed at a pneumoperitoneal insufflation pressure of 12-15 mmHg, derived from standard practice used during laparoscopic surgeries. Abdominal insufflation with carbon dioxide causes a multitude of known physiologic changes including increased peak airway pressures, depressed cardiac output, oliguria, and systemic acidosis, many of which show dose-dependent improvement with the reduction of intraoperative pressures.

Reducing intraperitoneal stretch with lower intra-abdominal pressures may also improve postoperative pain and facilitate earlier hospital discharge as evidenced by studies in general surgery comparing outcomes following laparoscopic cholecystectomy. Despite these results, few surgeons perform RALP at reduced pressure likely due to habit or the perceived concern for poorer visibility, compromised hemostasis, and/or technical difficulty. Furthermore, some have even proposed performing RALP at an increased pressure of 20 mmHg in an effort to achieve better hemostasis despite other physiologic consequences. There remains a paucity of data exploring the feasibility and potential benefits of performing RALP at low insufflation pressures, and no studies have explored how high the pneumoperitoneal pressure must be to perform RALP or, in other words, the minimum pressure that is adequate.

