### **1.2 – Specific Aims/Rationale**

We propose a study comparing insufflation pressures during RALP. Standard pressure is typically 15 mmHg, while in our previous study we determined that 6 mmHg is possible routinely. Therefore, we plan to compare the clinical outcomes of patients at a pneumoperitoneal pressure of 15 versus 6 mmHg.

***Aim #1)*** Compare average postoperative pain medication use between groups, as measured in total morphine equivalents (MME) over time at pre-specified time intervals through follow-up at 1 week.

***Aim #2)*** Compare average and maximum postoperative pain scores between groups, as measured using the self-reported 11-point numerical rating scale (NRS), over time at pre-specified time intervals through discharge.

Time intervals for Aims #1 & 2 are as follows: during the post-anesthesia care unit (PACU) stay, the first 4 hours on the floor, next 8 hours, and the following 8 hours; as well as the final score immediately prior to discharge.

***Aim #3)*** Compare operative ventilation as measured by average tidal volume (ml) between groups.

Tidal volume is the lung volume representing the normal volume of air displaced between normal inspiration and expiration when extra effort is not applied (i.e., normal/resting breathing), and is measured continuously throughout the procedure by Anesthesia. Potential patient benefits to a lower pneumoperitoneal insufflation pressure include decreased postoperative pain and improved intraoperative ventilation.

***Aim #4)*** Compare average length of stay (typically 0-1 days) between groups.

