Intraoperative	

1. Details of the surgical procedure (free text)

2. Port number/size(s)/locations (standard protocol -or- deviation from standard protocol) – if deviation, explain

3. Continuously recorded values (only means/standard deviations recorded in REDCap) – as measured by Anesthesia

a. End tidal CO2 (mmHg)

b. O2 saturation (%)

c. Respiratory rate (bpm)

d. Blood pressure (mmHg)

e. Heart rate (bpm)

f. Tidal volume (ml)

g. PIP (peak inspiratory pressure) (mmHg)

h. PEEP (positive end-expiratory pressure) (mmHg)

4. Core body temperatures (F) – as measured by Anesthesia

a. After trocar placement (baseline)

b. 30 minutes

c. 60 minutes

d. End of procedure

5. Insufflation time (minutes)

6. Insufflation pressure (6 or 15 mmHg)

7. Increased pressure episodes necessary to successfully complete the procedure (# times)

a. Time of each adjustment (hh:mm)

b. Level of each adjustment (mmHg)

8. Significant loss of pneumoperitoneum (# times)

a. Time of each adjustment (hh:mm)

b. Level of each adjustment (mmHg)

9. Pressure range (lowest and highest; mmHg)

10. Smoke evacuation quality (below average, average, above average)

11. Total amount of gas used during the procedure (l)

12. Scope cleanings (#)

13. Malfunctions of the AirSeal iFS or control devices (# times)

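### Aim 3 judges operative ventilation on mean tidal volume alone, which cannot show a change in respiratory mechanics if the anesthesia team holds tidal volume; the plan does not state the ventilation mode

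*Combined protocol and SAP*

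**What the plan says.** Section 1.2 sets Aim 3 as "Compare operative ventilation as measured by average tidal volume (ml) between groups". Section 2.4 repeats the aim, says that tidal volume "is measured continuously throughout the procedure by Anesthesia", and plans one comparison: "The average tidal volume for each patient will be compared between the two groups", by t-test or Mann-Whitney U test. The other three aims concern opioid use, pain scores and length of stay, so no aim names an airway-pressure measure.

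Three other places bear on this:

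- **Section 1.1 (Background)** says that insufflation causes "a multitude of known physiologic changes including increased peak airway pressures", followed by circulatory, renal and acid-base effects.
- **Section 2.2, Table 1 (Intraoperative, item 3)** lists PIP and PEEP beside tidal volume among the continuously recorded values, with "only means/standard deviations recorded in REDCap". The text after the table says that the PI, working with analysts, calculates these summaries for each patient.
- **Section 2.4, opening paragraph,** gives a general rule that continuous variables are compared between the groups by the same two tests. It names no variable.

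The supplied text states no ventilation mode. Section 2.3 says only that clinical decisions follow standard practice. The data forms in the appendices are not part of the supplied text.

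**The concern.** Sections 1.2, 2.3 and 2.4 name better ventilation during surgery as one of two potential benefits to patients, and Aim 3 is the only aim that tests it. Both sections that state Aim 3 define tidal volume in terms of resting breathing, yet it is measured under anesthesia, where it may be a setting and not a response. If it is held at a chosen value, easier ventilation lowers the pressure needed and leaves the volume where it was set. Aim 3 could then be null despite a real change in mechanics. If staff adjust the volume, a difference could partly reflect their settings.

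A PIP comparison made under the general rule would help a reader. But its weight against the tidal volume result would be decided after the data are seen, and the PI, who helps to summarise these recordings, knows the pressure used.

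**Working it through.** **The plan's own figure.** There is no sample-size or power figure for Aim 3. The trial is sized on a pain score: (3.9 − 3.2)/1.4 = 0.5 SD. A two-sided t-test at 0.05 with 90% power needs 85.03, rounded up to 86 per group, or 172 in total; 172/0.9 = 191.1, rounded up to 192. The stated size reproduces. For any roughly normal per-patient mean, 86 per group detects (1.960 + 1.282) × √(2/86) = 0.49 SD with 90% power. The documents give no SD for tidal volume, PIP or PEEP, so this cannot be turned into ml or mmHg.

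**Mechanism.** Write TV = C × (PIP − PEEP − R), where C is compliance and R is resistive pressure.

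- TV held: a change in C moves PIP only. TV has the same distribution in both arms, so its test rejects 5% of the time.
- Pressure fixed: a change in C moves TV, and PIP carries no information.

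**Illustration.** Every input here is assumed; none is in the documents. TV when held is N(500, 60) ml. Control mean pressure above PEEP when TV is held is 25 mmHg, of which R is 5 or 8 (SD 1.5). PEEP is 5 (SD 1). Control compliance is centred on 500/(25 − R), lognormal, CV 25% or 35%. When pressure is fixed, pressure above PEEP is N(25 − R, 3) with no resistive part. There are 86 per group, a two-sided t-test at 0.05, and the same share of patients with TV held in both arms. Ranges run from CV 35% with R = 8 to CV 25% with R = 5.

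| True compliance at 6 mmHg | TV held in | Power: TV | Power: PIP | Power: TV/(PIP − PEEP) |
|---|---|---|---|---|
| ×1.25 | all | 5% | 96–99.8% | 98–100% |
| ×1.25 | half | 69–88% | 46–78% | 89–99.8% |
| ×1.25 | none | 96–99.9% | 5% | 99–100% |
| ×1.10 | all | 5% | 36–56% | 40–65% |
| ×1.10 | half | 18–28% | 12–20% | 28–56% |
| ×1.10 | none | 36–57% | 5% | 43–71% |

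TV alone and PIP alone each become uninformative in one setting. With equal mode use in the arms, the ratio does not.

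**Limits of the ratio.** It understates the change when TV is held, because PIP includes R. With R = 5, the elastic part falls from 20 to 20/1.25 = 16, so the ratio goes from 500/25 = 20.0 to 500/21 = 23.8 (+19%). With R = 8, 17/1.25 = 13.6 and 500/21.6 = 23.1 (+16%).

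It also depends on mode. With no true effect and R = 5, the central ratio is 500/25 = 20 when TV is held and 500/20 = 25 when pressure is fixed. If TV is held in 75% of one arm and 50% of the other, the arm means are 0.75 × 20 + 0.25 × 25 = 21.25 and 0.5 × 20 + 0.5 × 25 = 22.5, a 6% difference produced by mode alone. With R = 8 the fixed-pressure value is 500/17 = 29.4, the arm means are 22.4 and 24.7, and the difference is about 10.5%. Simulated on the same assumptions with no true effect, false positives are about 32–47% for the ratio and 39–58% for PIP, against about 5% for tidal volume.

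**Multiplicity.** Section 2.4 tests everything at 0.05. Two independent tests give 1 − 0.95² = 9.75% for at least one false positive, and three give 1 − 0.95³ = 14.3%. The upper bounds under any dependence are 10% and 15%.

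**The case against.** The strongest objection is that the harm rests on a fact the documents do not supply. If pressure is fixed, tidal volume is the informative measure and PIP is the uninformative one. This stands. A reader might infer that Aim 3 is bound to be null or that tidal volume is the wrong endpoint; without a stated mode, neither follows.

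Second, the general rule in Section 2.4 already covers a comparison of PIP and PEEP, which are continuous variables in Table 1. This also stands. A reader might infer that airway pressures will go unanalysed, and the text does not support that. What is missing is their role in the ventilation conclusion, and the rule would not by itself produce the ratio, which is listed nowhere.

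Third, the ratio might seem to settle the matter whatever the mode. It does not. The trial is single-blinded, the envelope is opened in the operating room, and nothing says that anesthesia staff are unaware of the arm, so equal mode use cannot be assumed. Unequal use can create a false difference, as shown above, or hide a true one. With compliance truly 25% higher and TV held in half of controls but all of the 6 mmHg arm, the central ratios are 23.8 against 22.5 (+6%) for R = 5, and 23.1 against 24.7 (−6%, the wrong direction) for R = 8. This limits the remedy and is why mode must be tabulated.

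Fourth, tidal volume is a defensible content choice, and the Background lists airway pressure as one effect among several. That is fair, but it does not remove the gap: the single measure chosen can be uninformative under a mode that the plan does not exclude.

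**Conclusion.** The point holds in a conditional form. Aim 3 rests its ventilation conclusion on mean tidal volume alone, and the supplied text does not establish that tidal volume is free to vary. If it is held, Aim 3 cannot detect a change in respiratory mechanics; that follows from the mechanism and needs none of the assumed values. If pressure is fixed, the planned test is informative. The size of the problem in this trial is unknown: the power figures rest entirely on assumed inputs and, for tidal volume, span 5% to 99.9% at a 25% rise in compliance. The other aims and the sample size are unaffected. The plan should be changed because the remedy is cheap and Aim 3 is the only test of a stated benefit. Confidence is medium.

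**What to change.** In Sections 1.2 and 2.4, under Aim 3:

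1. Keep mean tidal volume and its planned test.
2. Pre-specify, as supportive measures compared by the same test, per-patient mean PIP and the ratio mean TV / (mean PIP − mean PEEP).
3. State that the three are read together and that no ventilation conclusion is drawn from tidal volume alone.
4. Tabulate ventilation mode by arm where the anesthesia record holds it. If mode differs between arms, report the PIP and ratio comparisons within mode. This records practice and does not alter it.
5. State the limits: the ratio understates a compliance change when tidal volume is held, and both PIP and the ratio can differ spuriously if mode use is unbalanced.

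The cost is a protocol and SAP amendment with IRB review, a registration update, and extraction of mode where available. The ratio needs no new patient measurement, since all three means are already planned for REDCap, and the sample size does not change. The extra comparisons are unadjusted at 0.05: the chance of at least one false positive under Aim 3 is 9.75% for two independent tests and 14.3% for three. The amendment should say so.

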**Aim #4) Compare average length of stay (typically 0-1 days) between groups.**

The average length of stay postoperatively will be compared between the two groups using independent sample t-test or Mann-Whitney U test, as appropriate. Also, the proportion of patients in each group who went home on day 1 versus day 0 will be compared using Chi-square test or Fisher's exact test, as appropriate. A difference of 10% in the proportion of patients will be considered clinically significant.

A p-value of less than 0.05 will be considered statistically significant for analysis. All of the analyses will be performed using SAS Enterprise Guide, version 7.1 (SAS Institute, Cary, NC).

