	

14. Estimated blood loss (EBL; ml)

15. Obturator artery manipulation (no, left, right, bilateral) – only on Case Sheet (Appendix F)

16. Console time (minutes from initial incision to closure)

17. Use of intraoperative pain medication

a. Fentanyl (y/n)

i. Dose (mg)

ii. Morphine equivalents (MME)

b. Toradol (y/n)

i. Dose (mg)

18. Pathology report

a. Pathological Stage

b. Clinical Stage (T1a-c, T2a-c, T3a-c)

c. Gleason Score (ranging from 6-10: 3+3=6, 3+4=7, 4+3=7, 3+5=8, 5+3=8, 4+4=8, 4+5=9, 5+4=9, 5+5=10)

d. Margins (positive/negative)

e. Extra prostatic extension (EPE; y/n)

f. Tumor quantification (%)

Postoperative (PACU & Floor)	

1. Recorded in PACU

a. Vital signs recorded in PACU setting

i. Time

ii. Respiratory rate (bpm)

iii. Blood pressure (mmHg)

iv. Heart rate (bpm)

v. Temperature (F)

b. Other PACU assessments

i. O2 saturation (%) (first recorded)

ii. Post-operative nausea and vomiting (y/n for each)

iii. Wound infection (y/n)

c. Time in PACU (hours)

i. Arrival & discharge times (hh:mm)

2. Recorded on Floor

a. Vital signs first recorded in non-PACU setting (i.e., on the floor)

i. Respiratory rate (bpm)

ii. Blood pressure (mmHg)

iii. Heart rate (bpm)

iv. Temperature (F)

b. Other non-PACU / Floor assessments

i. Labs drawn (y/n)

1. Serum creatinine (mg/dl; date)

2. Hemoglobin (g/dl; date)

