### **2.3 – Study Design**

We propose a prospective, randomized, controlled trial comparing insufflation pressures during RALP. Standard pressure is typically 15 mmHg, while in our previous study we determined that 6 mmHg is possible routinely; therefore, we plan to compare the clinical outcomes of patients between pneumoperitoneal pressures. Potential study subjects will be identified by reviewing clinic schedules at the PI's Robotic Urology practice at Dublin Methodist Hospital. As part of the new patient paperwork, patients will be mailed an informational letter (see Appendix G) highlighting active research studies for review prior to the index routine visit with the PI.

All patients that are candidates for RALP will be screened by the Clinical Research Coordinator (CRC) prior to their surgery planning visit. Once a patient is identified as meeting all study criteria, they will be approached by the CRC at their visit and the study will be thoroughly explained. After the patient has had all their questions answered and has agreed to participate in the study, informed consent will be obtained, followed by randomization in a 1:1 single-blinded fashion to either a pneumoperitoneal insufflation pressure of 15 mmHg (control group) or 6 mmHg (study group). The randomization allocation schedule will be developed by staff from the OhioHealth Research & Innovation Institute (OHRI), and will be hidden from the investigators until directly prior to surgery to prevent bias. Specifically, the CRC will open the randomization envelope in the operating room (OR) immediately prior to surgery. Randomization will be blocked to prevent selection and accidental bias.

Patients will be prepared for surgery per standard institutional policy and routine practice; the only difference in surgical technique will be the insufflation pressure applied. All ports will be placed

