Similar to aim 1, postoperative pain scores will be assessed at following time points: during the PACU stay, during the first 4 hours on the floor, next 8 hours, and the following 8 hours, as well as the final scores immediately prior to discharge (or via phone call if discharged same-day). There will be only one measurement of pain at each bodily location during the PACU stay, as well as at discharge. However, the average and maximum postoperative pain scores will be calculated for each of the time intervals (the first 4 hours on the floor, next 8 hours, and the following 8 hours). The comparison of average and maximum scores at each time point between the two groups will be performed using independent sample t-test or Mann-Whitney U test, as appropriate.

The association between patient demographic or clinical characteristics and differences in medication use or pain scores will be assessed using multivariate regression. The appropriate type of regression (logistic or linear) used will be determined after data collection is complete.

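### Aim 4 tests same-day against next-day discharge without adjusting for when the operation started, which gives up some precision on a calendar-day endpoint

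*Combined protocol and SAP*

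**What the plan says.** Section 2.4, Aim #4, gives two comparisons, neither with a covariate. For length of stay: "The average length of stay postoperatively will be compared between the two groups using independent sample t-test or Mann-Whitney U test, as appropriate". For the day of discharge: "the proportion of patients in each group who went home on day 1 versus day 0 will be compared using Chi-square test", with Fisher's exact test as the alternative. The yardstick is "A difference of 10% in the proportion of patients will be considered clinically significant", and for all analyses "A p-value of less than 0.05 will be considered statistically significant for analysis".

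Table 1 records length of stay in days, and section 2.3 equates Day 0 with same-day discharge. On allocation, section 2.3 says "Randomization will be blocked to prevent selection and accidental bias". It gives no block size and names no stratification factor. The envelope is opened in the operating room directly before surgery.

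The only regression in the plan appears under Aim #2: "The association between patient demographic or clinical characteristics and differences in medication use or pain scores will be assessed using multivariate regression". Discharge and length of stay are outside it.

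Table 1 lists PACU arrival and discharge times and the hospital discharge date and time. It does not list the clock time at which the operation or anesthesia started. Case order is mentioned nowhere.

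**The concern.** The endpoint is cut at the end of the calendar day. A patient whose operation starts early has more hours to go home on day 0 than one whose operation starts late, whatever the insufflation pressure. That follows from the definition of the endpoint. One surgeon does every case, so on any day with more than one case the start times must differ.

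Because the envelope is opened just before surgery, start time is in practice settled before allocation. It is therefore a legitimate baseline covariate. Leaving it out keeps its variation in the error term and leaves the observed difference exposed to a chance excess of late cases in one arm. Shorter stay is one of the trial's four aims and part of its stated motivation in section 1.1.

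**Working it through.** **The plan's own figure.** Section 2.4 sizes the trial on pain scores: means 3.2 and 3.9, SD 1.4, alpha 0.05, power 90%. The effect size is 0.7/1.4 = 0.5. The two-sided t-test calculation gives 85.03, rounded up to 86 per arm, 172 in total; 172/0.9 = 191.1, rounded up to 192. Both figures reproduce. There is no sample size or power figure for Aim 4.

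**Assumptions for Aim 4, none of them in the documents.** There are 96 per arm (192/2, so no losses). Half of cases are late, and the overall day-0 rate is 55%. The early-minus-late gap g in day-0 discharge is 20, 40 or 60 points, that is early/late rates of 65/45, 75/35 or 85/25%. The plan's 10% is read as 10 percentage points; it does not say absolute or relative.

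**Chance imbalance.** With late share q, the between-arm difference in late share has SD = √(2q(1−q)/n) = √(2 × 0.25/96) = 0.072, or 7.2 points. Multiplying by g gives the SD of the shift in the crude day-0 difference:

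| Gap g | SD of shift | 95% range (±1.96 SD) | Chance of a shift of 5 points or more |
|---|---|---|---|
| 20 | 1.4 | ±2.8 | about 0.1% |
| 40 | 2.9 | ±5.7 | 8% |
| 60 | 4.3 | ±8.5 | 25% |

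With 30% of cases late the 95% ranges are ±2.6, ±5.2 and ±7.8. With 86 per arm and half late they are ±3.0, ±6.0 and ±9.0.

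**Blocking.** Blocks balance the arm totals, not late cases within arms. If cases alternate early and late and envelopes are used in order, the simulated imbalance SD is 10.5, 8.4, 7.9 and 7.7 points for blocks of 2, 4, 6 and 8. That is no smaller than the 7.2 above.

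**Precision and power at a true 10-point difference.** Crude SE = √(2 × 0.55 × 0.45/96) = 0.0718. Stratifying removes the between-stratum variance 0.25g², so SE = √(2 × (0.2475 − 0.25g²)/96). Power is approximately Φ(0.10/SE − 1.96).

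| Analysis | SE (points) | Power by formula | Power by simulation |
|---|---|---|---|
| Crude | 7.2 | 28.5% | 28-29% |
| Stratified, gap 20 | 7.0 | 29.5% | about 29% |
| Stratified, gap 40 | 6.6 | 33.0% | about 33% |
| Stratified, gap 60 | 5.7 | 41.5% | about 41% |

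The simulation used 20,000 trials per setting and compared a crude test with Cochran-Mantel-Haenszel. A separate run of 8,000 trials gave 31%, 33% and 42% stratified. In that run, with no true difference, both tests rejected in about 5% of trials.

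**Aim 4 overall.** For a 10-point difference starting from a lower rate between 30% and 80%, crude power with 96 per arm is 28-49%. Reaching 80% power would need 199-388 per arm.

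**The case against.** The strongest reply is that nothing here is an error. An unadjusted test of a binary outcome in a 1:1 randomised trial is valid, and chance imbalance in any prognostic factor is already reflected in its standard error. Covariate adjustment could be suggested for almost any crude comparison. The documents give no number of cases per day, spread of start times, same-day discharge rate or early-late gap. Section 1.1 ties same-day discharge to patients meeting criteria, not to the clock. At a 20-point gap the gain is about one point of power.

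All of that stands, and it limits the size of the point. It does not remove it: the mechanism is built into a calendar-day endpoint, and the remedy is specific and inexpensive.

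A reader might infer more than the documents support:

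- **That case order biases Aim 4.** Allocation is revealed just before surgery and the crude test holds its level, so it does not.
- **That imbalance could readily produce or hide most of a 10-point difference.** A shift of even 5 points has a chance of about 0.1% to 25% over the assumed gaps.
- **That start time is the strongest predictor of same-day discharge.** No figure in the documents shows this.
- **That the time stamp is already in the dataset.** Table 1 does not list it. The minute-by-minute anesthesia export is described as eight physiological variables, reduced to means and SDs for REDCap.
- **That case order sharply erodes power.** Power calculated at a fixed odds ratio gives this impression. At an odds ratio of 2.0, the implied risk difference is 15.6 points with control rates of 60/30% (early/late) but only 11.1 points with 80/20%. The smaller difference explains the fall in crude power; at a fixed 10 points it stays at 28-29%.

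**Conclusion.** The point holds as one of efficiency. Aim 4 leaves out a baseline factor that, by the endpoint's definition, bears on whether a patient can count as day 0, and nothing in the allocation or the analysis compensates. Under the stated assumptions the gain from adjustment is negligible at a 20-point gap and moderate at 60. The exposure to chance imbalance follows the same gradient and becomes material against a 10-point yardstick at gaps of 40 points or more. Where this trial lies in that range cannot be told from the documents.

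Adjustment would not rescue Aim 4. Power for 10 points stays well below 80% at every gap examined, because the trial was sized on pain scores. That is the larger weakness of this aim.

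**What to change.** 1. Add operating-room or anesthesia start time to Table 1 and REDCap as a new field, taken from the anesthesia record. Do not use PACU arrival: it falls after randomisation and includes the length of the operation, which the assigned pressure could affect.
2. In section 2.4, Aim #4, pre-specify a Cochran-Mantel-Haenszel test stratified by start-time category, with a stratified risk difference and its confidence interval. Define the categories (for example first case versus later case) before outcomes are seen, because an adjustment chosen after an imbalance has been noticed carries little weight.
3. Use the same covariate in the length-of-stay comparison.
4. Keep the unadjusted Chi-square or Fisher test as a sensitivity analysis, and state whether the 10% is absolute or relative.

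The cost is one extra data field and a few sentences of analysis text, with no added patients or procedures. The downside is that the gain may be small if the early-late gap is small.
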